January 16, 2022

Administration of follicle-stimulating hormone (FSH) and low dose human chorionic gonadotropin (hCG) for oocyte maturity while decreasing hCG exposure in In Vitro fertilization (IVF) cycles

NCT02310919

Study Protocol

Specific Aims

Primary Aim:

1) To determine if concomitant low dose hCG (1500 IU) and 450 IU FSH for oocyte maturation trigger is non-inferior to the standard hCG alone in total fertilization proportion (i.e. total competent proportion), according to the primary outcomes involving maturation and fertilization:

Total fertilization proportion (i.e. total competent proportion), defined as the number of fertilized oocytes (2PN) divided by the total number of oocytes retrieved, will be compared between the two treatment groups.

2) To further assess the outcomes of oocyte recovery and developmental competence of the mature oocytes the following will be compared between the two treatment groups:

- a) Oocyte recovery
- b) Oocyte maturity
- c) Fertilization rate
- d) Embryo quality
- e) Pregnancy rates

3) To compare serum and follicular post-trigger steroid hormones levels of estradiol, progesterone, hCG, FSH LH, and vascular endothelial growth factor (VEGF) between the two treatment groups at different times points:

- a) 12 hours after trigger (T+1), at oocyte retrieval (T+2), and 5 days after trigger (T+5) to assess serum levels of, as appropriate, based on the study visit day.
- b) Follicular fluid from the first aspirate of a dominant follicle on each ovary at retrieval

Secondary Aim: To determine if symptoms of OHSS are decreased with low dose hCG (1500 IU) and 450 IU FSH compared to standard hCG dose alone.

Compare symptoms related to OHSS using the following outcomes:

- 1) The change in bloating scores prior to trigger and after trigger
- 2) The change in abdominal circumference prior to trigger and after trigger
- 3) The change in body weight prior to trigger and after trigger

Experimental Design and Methods:

Study population:

The target population includes female patients undergoing IVF. All eligible female patients will be asked to join the study. Patients receiving any type of stimulation protocol for IVF will be offered participation in the study. Study participants will be recruited from the Reproductive Endocrinology Clinic at University of California at San Francisco Center for Reproductive Health.

Inclusion/Exclusion Criteria:

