Gonadotropin medications will be started as designated by the patient's primary doctor and baseline ultrasound is performed. Ultrasounds will be performed and serum estradiol (E2) will be checked as determined by the patient's primary doctor. Gonadotropin dose will be adjusted based on ultrasound findings and serum E2 level as needed to be determined by the patient's primary doctor. Gonadotropin injections will be continued until ovulation trigger.

The day of administration of ovulation trigger will be determined by the patient's primary doctor.

Guidelines for the experimental protocol:

Study participants will receive a syringe on the day of ovulation trigger containing either the standard dose of hCG or low dose hCG + FSH according to the randomization. The subjects will be triggered with the following:

- a) Standard dose of hCG (10,000 IU or 5,000 IU) or
- b) Low dose of hCG 1,500 IU SQ + FSH 450 IU SQ

For the control arm, the standard hCG dose will be given based on the E2 level on the day of ovulation trigger. If the E2 level is less than 3,500 pg/ml, then the trigger will be 10,000 IU of hCG. If the E2 level is more than 3,500 pg/ml but less than 5,000 pg/ml, then the trigger will be 5,000 IU.

On the day of ovulation trigger, the subject's body weight and abdominal circumference will be measured. The subject will also complete a questionnaire regarding her current symptoms. In

addition to the standard of care estrogen lab, residual blood from that draw will be retained by the study for an additional lab to assess additional hormone levels. Subjects will return 12 hours after trigger (T+1), at oocyte retrieval (T+2), and 5 days after trigger (T+5) to assess serum levels of estradiol, progesterone, hCG, FSH, LH, and vascular endothelial growth factor (VEGF), as appropriate, based on the study visit day.

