In order to avoid failure of ovulation trigger, the post trigger day serum hCG will be determined and communicated to the unblinded clinician. If the serum hCG level is less than 18 IU/L, then the subject will be excluded from the study and assessed by their primary doctor for possible re-trigger. If the ovulation trigger fails then administration of a second trigger medication is the standard of care.

Assessment of OHSS related symptoms:

To assess the incidence of OHSS related symptoms, patients will be evaluated objectively by a change in the abdominal circumference as well as subjectively by clinical symptomatology based on patient's bloating symptoms using a questionnaire.

Prior to starting the stimulation, the abdominal circumference (C) and body weight (BW) will be measured in centimeters at the baseline ultrasound visit (C_{baseline}, BW_{baseline}). Also, the abdominal circumference (C) and body weight (BW) will be measured in centimeters on the day of ovulation trigger. Five days after the oocyte retrieval the abdominal circumference and body weight will again be measured in centimeters (C_{stimulated}, BW_{stimulated}). The difference in the abdominal circumference and body weight will be calculated.

The patient's clinical symptoms will be evaluated based on a bloating score reported by each patient on the day of ovulation trigger and then 5 days after the oocyte retrieval will be determined. A venipuncture will also be obtained for hormone assays 5 days after oocyte retrieval.

The bloating score will range from 0-5, and will be determined as follows:

0 - No bloating

1 - Mild bloating. Able to continue daily activities without discomfort.

2 - Mild to moderate bloating. Able to continue daily activities but with mild discomfort.

3 - Moderate bloating. Able to continue daily activities but with moderate discomfort.

4 - Moderate to severe bloating. Difficulty performing daily activities.

5 - Severe bloating. Abdomen feels very tense and unable to perform daily activities.

The difference in the bloating score will be calculated.

Sample Collection:

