Analyses will be performed based on intention-to-treat (ITT). Using the standard trigger as reference, the relative risk and associated 95% confidence interval (CI) for the probability of laboratory outcomes was calculated using log-binomial regression models. Generalized estimating equations (GEE) with an exchangeable correlation structure was applied to account for clustered data (i.e. oocytes and embryos originating from the same patient). Continuous laboratory outcomes were compared using generalized linear modeling with log link function. For pregnancy outcomes, relative risk and 95% CI were calculated to estimate effect size. Hormone concentrations were compared using Wilcoxon rank sum test. For the non-inferiority hypothesis testing of the primary outcome, a one-sided 95% CI was constructed for the relative risk. The alternative trigger will be considered non-inferior to the standard trigger if the lower bound of the one-sided CI of the relative risk is not less than 0.8 (i.e. risk reduction limit of 20%). For secondary outcomes, the statistical significance was based on a two-sided alpha of 0.05. Data were analyzed using SPSS version 28.0.1.0 (Statistical Package for Social Sciences; Chicago, IL).

For the secondary aim evaluating OHSS related symptoms, the abdominal circumference, body weight, and bloating score will be analyzed using t-tests to determine if the change is significantly different between the trigger groups. For these secondary aim outcomes, we do not expect to have sufficient numbers of events to conduct a formal analysis.

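### The OHSS-symptom changes are tested by unadjusted t-tests although the trigger-day values are collected; adjusting for them would cost nothing and could sharpen the bloating comparison

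*Combined protocol and SAP*

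**What the plan says.** All references are to the combined protocol and SAP.

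- **Test.** The last paragraph of Statistical analysis says that the three symptom measures "will be analyzed using t-tests to determine if the change is significantly different between the trigger groups". No covariate is named for them. The same paragraph adds that too few events are expected for a formal analysis of these outcomes. The paragraph before it sets the criterion: "For secondary outcomes, the statistical significance was based on a two-sided alpha of 0.05".
- **Endpoint.** Specific Aims (Secondary Aim) defines each endpoint as a before-to-after-trigger change, for example "The change in bloating scores prior to trigger and after trigger".
- **Trigger-day values.** Guidelines for the experimental protocol states: "On the day of ovulation trigger, the subject's body weight and abdominal circumference will be measured". Assessment of OHSS related symptoms adds "a bloating score reported by each patient on the day of ovulation trigger".
- **Scale.** "The bloating score will range from 0-5", and "The difference in the bloating score will be calculated".
- **Timing.** Patients are randomized on the trigger day and take the syringes away to inject at an assigned time. With the before-trigger definition in Specific Aims, this makes the trigger-day measurements pre-treatment values.

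**The concern.** Subtracting the trigger-day value fixes the slope of the after value on the before value at 1. On a self-rated 0-5 score a slope below 1 is plausible, partly because the scale is bounded: a woman who scores 4 at trigger can rise by only 1 point. When the true slope is below 1, subtraction removes too much. The change score then carries extra noise. If one arm happens to start higher, its estimated change is pushed the opposite way.

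At stake is the precision of the plan's only stated comparison of OHSS symptoms, in a trial of about 50 women per arm whose size was set for a different outcome. The covariate that would recover this precision is already in the data.

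**Working it through.** **1. The plan's own figure.** Sample size and power analysis gives about 50 per arm for the fertilization outcome. Inputs: proportion 0.5, margin 0.10, one-sided alpha 0.05, power 0.8, 15 oocytes per woman, intra-cluster correlation 0.1.

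- Oocytes per arm: (1.645 + 0.842)² × 2 × 0.25 / 0.10² ≈ 309.1, rounded up to 310.
- Design effect: 1 + 14 × 0.1 = 2.4.
- Women per arm: 310 × 2.4 / 15 = 49.6, so 50.

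The figure reproduces. No sample size is given for the symptom endpoints, so 50 per arm is simply what is available to them.

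**2. Formulas.** Let the before SD be 1, the after SD be k, the correlation r and the slope b = rk.

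- Variance factor, change score: 1 + k² − 2rk. With k = 1 this is 2(1 − r).
- Variance factor, ANCOVA: k²(1 − r²). With k = 1 this is 1 − r².
- Difference between them: (1 − b)². With k = 1, the ratio ANCOVA/change is (1 + r)/2.

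Estimating the slope costs ANCOVA a factor of about 1 + 1/96 at this size, or 1%, which the table ignores.

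**3. Variance reduction from ANCOVA.** Both r and k are assumptions.

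| After/before SD ratio k | r = 0.3 | r = 0.4 | r = 0.5 | r = 0.7 |
|---|---|---|---|---|
| 0.8 | 50% | 46% | 43% | 37% |
| 1.0 | 35% | 30% | 25% | 15% |
| 1.25 | 22% | 16% | 11% | 2% |
| 1.5 | 13% | 8% | 4% | 0.2% |

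Example, k = 1.5 and r = 0.4: 2.25 × 0.84 = 1.89 against 3.25 − 1.20 = 2.05. The ratio is 0.92, a reduction of 8%.

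For weight and circumference with k = 1, the reduction is 5% at r = 0.9, 2.5% at r = 0.95 and 1% at r = 0.98. The last is cancelled by the cost of estimating the slope.

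**4. Power.** Assume a true difference of 0.5 SD, k = 1, 50 per arm and two-sided 0.05. The SE is √(2 × factor / 50) and power is Φ(0.5/SE − 1.96).

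| r | t-test on change | ANCOVA |
|---|---|---|
| 0.3 | 0.561 | 0.746 |
| 0.4 | 0.626 | 0.779 |
| 0.5 | 0.705 | 0.823 |
| 0.7 | 0.898 | 0.938 |

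Ignoring the trigger-day value altogether gives 0.705, so with equal SDs the change score does worse than that below r = 0.5. In general the threshold is r = 1/(2k), which is 0.33 at k = 1.5.

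**5. Chance imbalance.** The trigger-day means of two arms of 50 differ by chance with SD √(2/50) = 0.20 SD. The change-score estimate moves by (b − 1) times the imbalance. With k = 1 and r = 0.4, an imbalance of 0.20 SD moves it by 0.6 × 0.20 = 0.12 SD in the opposite direction.

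This is the loss in step 3 seen conditionally. The estimator variances are 0.04 × 1.2 = 0.0480 (change) and 0.04 × 0.84 = 0.0336 (ANCOVA). They differ by 0.0144, which is 0.12².

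**6. Bounded score.** Rounded 0-5 scores were simulated with 50 per arm and 6,000 trials per setting. The assumed latent means were 1.8 before and 2.2 after, with SD 1.3 and r = 0.5.

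- Variance ratio ANCOVA/change: 0.75.
- Power for a latent shift of 0.7 points: 71% (change) against 83% (ANCOVA).
- Rejection with no effect: 5.1% against 4.7%.
- Slope of the estimate on baseline imbalance: −0.52 against 0.02.

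The equal-SD formula therefore carries over to a bounded, rounded score in this setting.

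**The case against.** **The planned test is not wrong.** This stands. Randomization makes the t-test on change unbiased on average, with type I error near 5%. A reader might infer a biased or invalid analysis; neither the documents nor the simulation support that.

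**Lost precision and carried imbalance are one harm.** This also stands. Steps 2 and 5 show that the imbalance term accounts for the whole variance difference, so it must not be counted twice. At r = 0.4 the 0.12 SD shift is about half the test's own SE, √(2 × 1.2 / 50) = 0.22 SD, which already includes it.

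**The size is not established.** This stands too. A reader might take 25% to 35% as the expected gain for bloating. The documents give no r, no SDs and no target difference. If some women become much more symptomatic than others, the spread after trigger may widen, the slope may approach 1 and the gain may nearly vanish. That is also an assumption. In the settings tried, ANCOVA was never materially worse.

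**The plan expects no formal analysis.** This stands only in part. The sentence gives a shortage of events as its reason, but these endpoints are measurements and scores rather than events, and the same paragraph names a significance test. It does not withdraw that test. It does confirm that no power was claimed.

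**Benefit can appear elsewhere.** A reader might infer that the symptom comparison is the trial's only chance to show an advantage of less hCG. Specific Aims also compares hCG, VEGF and other hormones between arms, so that reading is too strong.

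**ANCOVA does not remove floor and ceiling effects.** Correct. Robust standard errors deal with unequal variance, not with a bounded scale, which is why a rank-based or ordinal sensitivity analysis is needed.

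**Conclusion.** The point holds as a free efficiency improvement, mainly for bloating, and not as an error. The plan collects a pre-treatment value of each measure and uses it in a way that is less precise than ANCOVA whenever the slope is below 1.

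For bloating, the range runs from a worthwhile gain (a quarter to a third of the variance at r = 0.3 to 0.5 with equal SDs) to a small one (4% to 13% over the same r at an SD ratio of 1.5). For weight and circumference it is minor under the assumptions of equal SDs and r of 0.9 or more. The direction is secure for any slope below 1; the size depends on an r and an SD ratio that the documents do not give. The non-inferiority conclusion on fertilization does not depend on this analysis.

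**What to change.** In Statistical analysis, replace the t-tests by ANCOVA for each of the three measures: post-trigger value regressed on arm and the trigger-day value of the same measure. Use robust standard errors and add a rank-based or ordinal sensitivity analysis for bloating. Report the adjusted mean difference with its 95% CI.

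Two definitions need reconciling in the same edit, because r and the slope depend on them:

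- **Follow-up visit.** It is five days after trigger in Guidelines for the experimental protocol, but five days after retrieval in Assessment of OHSS related symptoms.
- **Earlier value.** Assessment of OHSS related symptoms also records circumference and weight before stimulation, and it does not say which earlier value enters the difference.

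Parts of the section are in the past tense. If the data have already been analysed, report the ANCOVA beside the planned t-test and label it as added later.

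The cost is a sentence or two of wording and one additional model per endpoint, with no new data, visits or participants.

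### The OHSS-symptom comparisons are planned as t-tests and then ruled out for too few events, and neither their follow-up date nor, for circumference and weight, their starting value is fixed

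*Combined protocol and SAP*

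**What the plan says.** The Secondary Aim asks whether OHSS symptoms are decreased, using three outcomes: the change from before to after trigger in bloating score, abdominal circumference and body weight.

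In the combined protocol and SAP, the last paragraph of Statistical analysis says that these outcomes "will be analyzed using t-tests to determine if the change is significantly different between the trigger groups". The next and final sentence reads: "For these secondary aim outcomes, we do not expect to have sufficient numbers of events to conduct a formal analysis".

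Assessment of OHSS related symptoms describes the measurements. It opens: "To assess the incidence of OHSS related symptoms, patients will be evaluated objectively by a change in the abdominal circumference", together with a bloating questionnaire scored 0 to 5. Circumference and weight have a first value: "Prior to starting the stimulation, the abdominal circumference (C) and body weight (BW) will be measured in centimeters at the baseline ultrasound visit". A second is taken on trigger day. Then: "Five days after the oocyte retrieval the abdominal circumference and body weight will again be measured in centimeters". What is analysed is given only as: "The difference in the abdominal circumference and body weight will be calculated". Bloating is a "bloating score reported by each patient on the day of ovulation trigger and then 5 days after the oocyte retrieval", so it has a single earlier value.

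The Specific Aims and Guidelines for the experimental protocol schedule a return visit five days after trigger (T+5). The latter section has circumference, weight and the bloating questionnaire taken at that visit.

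**The concern.** A test of whether a change is significantly different between arms is a formal analysis. The following sentence says that none is expected for the same outcomes, and gives a reason that belongs to rare binary endpoints. Circumference, weight and a 0 to 5 score give a value for every patient who is measured, so no event count governs them.

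These three outcomes are the whole of the Secondary Aim. As written, a p-value could be read as a planned test or as a description, and a null result could be put down to few events when the real limit is the width of the interval. Nor can the reader tell exactly which two time points a reported change spans.

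**Working it through.** **1. Are the outcomes events?** The Secondary Aim defines all three as changes. The OHSS assessment section gives two physical measurements and a six-level score, with no cut-off that turns any of them into an event. The word incidence appears there, but it is assessed by change in circumference and by the questionnaire. The events rationale therefore matches nothing defined in the document.

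**2. Time points side by side.**

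| | Specific Aims and experimental guidelines | OHSS assessment section |
|---|---|---|
| Earlier value, circumference and weight | Before trigger (aims); measured on trigger day (guidelines) | Pre-stimulation visit (labelled baseline) and trigger day |
| Earlier value, bloating | Before trigger (aims); symptom questionnaire on trigger day (guidelines) | Trigger day |
| Follow-up | Five days after trigger (T+5) | Five days after retrieval |

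Retrieval is 36 h after trigger, so five days after retrieval is 36 + 5 × 24 = 156 h after trigger. The time of T+5 depends on how it is counted:
- Literally five days after trigger: 5 × 24 = 120 h, a gap of 156 − 120 = 36 h.
- By the document's own labels, with T+1 at 12 h and T+2 at retrieval (36 h), each step is 24 h. T+5 is then 12 + 4 × 24 = 108 h, a gap of 156 − 108 = 48 h.

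The two dates are therefore about 1.5 to 2 days apart.

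**3. The plan's own sample size.** It is set for the primary outcome: proportion 0.5, margin 0.1, one-sided alpha 0.05, power 0.8, 15 oocytes per patient, intra-cluster correlation 0.1.
- Oocytes per arm: (1.645 + 0.842)² × (0.25 + 0.25) / 0.1², which rounds up to 310.
- Design effect: 1 + (15 − 1) × 0.1 = 2.4.
- Patients per arm: 310 × 2.4 / 15 = 49.6, so 50. The stated figure reproduces.

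No sample-size or precision figure is given for the symptom outcomes.

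**4. What 50 per arm gives for a t-test on change.** Units are SDs of the change, because the document gives no SD. The test is unadjusted, two-sided at 0.05. The 95% CI half-width is t(0.975, 2n − 2) × √(2/n). The difference detectable at 80% power is approximately (1.960 + 0.842) × √(2/n), refined with the noncentral t. The sizes 45 and 40 are assumed losses.

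| Measured at both times, per arm | CI half-width | Detectable, approximate | Detectable, noncentral t |
|---|---|---|---|
| 50 | 1.984 × 0.200 = 0.397 | 0.560 | 0.566 |
| 45 | 1.987 × 0.211 = 0.419 | 0.591 | 0.597 |
| 40 | 1.991 × 0.224 = 0.445 | 0.627 | 0.634 |

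Only the number of patients and the SD enter these formulas.

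**5. What adjustment could add.** Assume equal SDs σ at trigger day and follow-up, with correlation r. A change score has variance 2σ²(1 − r) per patient, and ANCOVA has residual variance σ²(1 − r²). The ratio is (1 + r)/2, times about (1 + 1/96) for estimating the slope with 50 per arm:
- r = 0.3: 0.65 × 1.0104 = 0.657
- r = 0.5: 0.75 × 1.0104 = 0.758
- r = 0.7: 0.85 × 1.0104 = 0.859
- r = 0.9: 0.95 × 1.0104 = 0.960
- r = 0.98: 0.99 × 1.0104 = 1.000

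A gain is plausible for bloating and may be nil for weight.

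**The case against.** The best defence is that the intent can be recovered. The events sentence may be left over from a planned analysis of OHSS incidence. The aim's before-and-after-trigger wording, with the trigger-day and T+5 measurements in the experimental guidelines, points to trigger day as the starting value, and it is the only earlier value common to all three outcomes. Much of this stands for the starting value. It does not close the question, because the OHSS section attaches baseline and stimulated labels to circumference and weight, which suggest the pre-stimulation visit. Nor does it rescue the events sentence, which refers expressly to these secondary-aim outcomes.

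Four stronger readings are tempting but unsupported.
- A reader might multiply two starting values by two follow-up dates and infer four competing analyses. The document describes one late visit, dated inconsistently; no section schedules both dates. If one visit is held, circumference and weight have at most two computable differences and bloating has one.
- A reader might infer an inflated false-positive rate from picking the better p-value. Nothing in the document says that this would be done.
- A reader might infer from "Data were analyzed using SPSS version 28.0.1.0" that the status of these tests was settled after the results were seen. That sentence is in the preceding paragraph; the OHSS paragraph is written prospectively.
- A reader might infer that the choice of starting value biases the comparison. The pre-stimulation value precedes randomization, and a trigger-day value taken before the injection precedes treatment, so the choice adds no bias. Whether patients excluded later for low post-trigger hCG leave the arms comparable is a separate matter.

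**Conclusion.** The contradiction over formal analysis is plain on the text, and the reason given for it is wrong. The follow-up date conflicts between sections by about 1.5 to 2 days, the range reflecting two ways of counting T+5. The starting value for circumference and weight is unclear, with the balance of the text favouring trigger day.

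The severity is minor. The outcomes and the test are already named, and the primary non-inferiority conclusion and its sample size are untouched. The precision figures assume an unadjusted comparison with 40 to 50 patients per arm measured at both times. Without an SD or an expected effect, they show neither that the comparisons are adequately powered nor that they are not.

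**What to change.** 1. **Status.** Delete the events sentence and state one status. Either keep the between-arm comparisons as planned secondary tests or, if outcomes by arm have already been seen and the status was not set beforehand, label them exploratory. In both cases report mean differences with two-sided 95% CIs and the number measured at both times. Give precision as the limit, using the detectable differences above for the number actually measured, and say that no SD was available.
2. **Time points.** Reconcile the follow-up visit date across the Specific Aims, the experimental guidelines and the OHSS assessment section. Name one starting value per outcome. The trigger-day value, stated to be taken before the injection, fits the Secondary Aim and is common to all three. Report the change from the pre-stimulation value, for circumference and weight, as a labelled sensitivity analysis.
3. **Adjustment.** If outcomes by arm are unseen, compare follow-up values by ANCOVA adjusted for the trigger-day value. Otherwise keep the t-test on change and report ANCOVA as a labelled sensitivity analysis.

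The cost is a few sentences, one consistent visit date and one covariate. No new measurement is needed.
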